8. EFFICACY ENDPOINTS

8.1 Primary Efficacy Endpoint

Change from baseline to week-8 post Relivion®DP treatment initiation in depressive symptoms as measured by HDRS-17 total score.

8.2 Secondary Efficacy Endpoints

Secondary efficacy endpoints include:

- **Proportion of responder subjects** - defined as the percent of subjects achieving at least 50% reduction from baseline in their HDRS-17 total score, 8 weeks post Relivion®DP treatment initiation.

- **Proportion of subjects achieving remission** - defined as the percent of subjects with HDRS-17 score≤7 at 8 weeks post Relivion®DP treatment initiation.
- **Change from baseline** to week-8 post Relivion®DP treatment initiation **in depressive symptoms** as measured by **MADRS** total score.

8.3 Tertiary Efficacy Endpoints

Tertiary Efficacy endpoints include:

- **Change from baseline** to 8 weeks post Relivion®DP treatment initiation **in the Clinical Global Impression Severity scale (CGI-S) score**.
- **Clinical Global Impression Improvement (CGI-I) score** over time **to Visit 4**.
- **Change from baseline** to week-8 post Relivion®DP treatment initiation **in the total score of the Quick Inventory of Depressive Symptomatology (self-rated)** (QIDS-SR-16).
- **Change from baseline** to week-8 post Relivion®DP treatment initiation **in depressive symptoms** as measured by **HDRS-21** total score.
- **HDRS-17 Total score** to week-8 post Relivion®DP treatment initiation.
- **Proportion of subjects achieving clinically substantial improvement in HDRS-17** - defined as the percent of subjects with reduction in HDRS-17 score of at least 7¹ points at 8 weeks post Relivion®DP treatment initiation.
- **HDRS-17 Category Shift from Visit 2 to Visit 4** – defined as the category change from baseline to week-8 post Relivion®DP treatment initiation in HDRS-17; Categories definition: 5: Very severe 26-52, 4: Severe 20-25, 3: Moderate 14-19, 2: Mild 13-8 and 1: 0-7 Remission.
- **Change from baseline Q-LES-Q score at Visit 4** – measured as the difference between the baseline and visit 4 Q-LES-Q percentage of maximum total scores.

¹ Rush AJ et al. Clinically Significant Changes in the 17- and 6-Item Hamilton Rating Scales for Depression: A STAR*D Report. Neuropsychiatric Disease and Treatment 2021;17:2333–2345

8.4 Safety Endpoints

Safety of the study device following study treatment: Incidence of adverse events and serious adverse events related or unrelated to the study device [Time Frame: up to 18 weeks post treatment initiation].

9. SIGNIFICANCE LEVELS AND HANDLING OF TYPE I ERROR

9.1 Type I error

The overall significance level for this study is 5% using two-tailed tests, except for treatment by site interaction that will be tested at a significance level of 10% and the test for early efficacy at the interim look.

9.2 Hierarchy Approach for The Primary and Secondary Endpoint Analysis

The hierarchy approach will be adopted for the primary and secondary endpoints to control type I error due to multiple endpoint testing. Thus, the primary endpoint will first be tested and only if $p \leq .05$, will the secondary endpoints be tested. For the three secondary performance endpoints, the Benjamini–Hochberg step-up method will be used to adjust the p-values. If the primary and the secondary endpoints are found statistically significant then the hierarchy will be extended to include the tertiary endpoints for the seven tertiary performance endpoints, the Benjamini–Hochberg step-up method will be used to adjust the p-values.

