**Controlling the Overall Type I Error:**

The hierarchy approach will be adopted for the primary and secondary endpoints to control type I error due to multiple endpoint testing. It is recognized that the ordering is important only with regard to rejection or non-rejection of the null hypothesis. Thus, the first endpoint will first be analyzed and only if  $p \leq 0.05$ , will the second endpoint be analyzed, and so on.

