We use conservative estimates of a 3.3-point difference with a standard deviation of 6 points. Calculations show that a sample size of 53 subjects per group (total 106) would provide 80% power at a 5% level of significance (two-sided) to detect the difference between treatment and sham groups.

Given our preliminary results, together with other companies clinically relevant data, we hypothesize that our statistical assumptions are aligned with competitive treatments for MDD.

The company anticipates that after randomization, but before the endpoint can be observed, up to 15% of the subjects will drop out from the study irrespective of study arm and success of treatment; thus, an adjustment for this drop-out rate is made and a sample size of 124 is required at the point of randomization.

We shall randomize an additional up to 36 subjects (30+15% dropout) in the age range 18-21 to assess efficacy in this age range as well.

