#### **Controlling the Overall Type I Error:**

The hierarchy approach will be adopted for the primary and secondary endpoints to control type I error due to multiple endpoint testing. Thus, the primary endpoint will first be tested and only if  $p \leq .05$ , will the secondary endpoints be tested. For the three secondary performance endpoints, the Benjamini–Hochberg step-up method will be used to adjust the p-values.

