1. INTRODUCTION

This Statistical Analysis Plan (SAP) is a more detailed companion to the Statistical Methods section of the study titled “The MOOD study – external Combined Occipital and Trigeminal Nerve Stimulation (eCOT-NS) for the treatment of Major Depressive Disorder (MDD)” and provides a comprehensive description of the analysis sets, endpoints, methods, and data analyses to be used. This SAP prevails when differences exist in descriptions or explanations provided in the protocol and the SAP. We shall address analysis strategies for the open label stage of the study. Addressed as well is a plan for prognostic factor analysis to identify potential baseline parameters related to the primary endpoint and its derivatives.

Relivion®DP, an external Combined Occipital and Trigeminal Afferent Stimulation (eCOT-AS) is proposed as a novel treatment for MDD. The combination of neuromodulation of both the occipital and the trigeminal nerve branches non-invasively is made possible for the first time, after having been successfully performed either separately or in invasive procedures.

Major depressive disorder is one of the leading causes of disability worldwide. However, treatment options are still limited, therefore new approaches are needed to enhance clinical improvement. The non-invasive combined neuromodulation of both the occipital and trigeminal nerve branches is a safe, self-administered novel technology with high potential for treating MDD patients. Based on this rationale, Neurorelief developed the Relivion®DP, a neuro-stimulator applying combined occipital and trigeminal afferent stimulation for treatment of major depressive disorder (MDD). Following completion of an early clinical study showing promising results, Neurorelief designed the proposed clinical trial to evaluate the safety and efficacy of the Relivion®DP in a two-arms controlled, double blinded randomized study.

The MOOD Study will evaluate the safety and efficacy of a self-administered treatment for MDD using an external combined occipital and trigeminal afferent stimulator (Relivion®DP).

This pivotal clinical investigation is intended to support future marketing applications (US FDA and CE) for Neurorelief’s Relivion®DP device.

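### SAP 9.2 presents its hierarchy as type I error control, but Benjamini-Hochberg controls only the false discovery rate within each family, and its seven tertiary endpoints contradict the eight listed

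*SAP*

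**What the plan says.** SAP 9.1: "The overall significance level for this study is 5% using two-tailed tests", with exceptions for the treatment-by-site interaction and the interim efficacy look.

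SAP 9.2 opens with "The hierarchy approach will be adopted for the primary and secondary endpoints to control type I error due to multiple endpoint testing". The primary is tested first at 0.05. The three secondaries (response, remission, MADRS change) then go through the Benjamini-Hochberg step-up. For the last step, SAP 9.2 says that "the hierarchy will be extended to include the tertiary endpoints for the seven tertiary performance endpoints", again with Benjamini-Hochberg. The condition set for this last step is: "If the primary and the secondary endpoints are found statistically significant".

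SAP 8.3 lists the tertiary endpoints, and SAP 11.5.5 gives an analysis for each of the same ones.

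Protocol 12.8.2 also names Benjamini-Hochberg for the three secondaries ("step-up method will be used to adjust the p-values"). The protocol synopsis describes a fixed sequence instead: only after one endpoint succeeds "will the second endpoint be analyzed, and so on". SAP 1 settles conflicts: "This SAP prevails when differences exist in descriptions or explanations provided in the protocol and the SAP". Benjamini-Hochberg therefore governs.

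**The concern.** There are two separate problems.

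**The label.** The gate from primary to secondaries does protect that step. Within a family, Benjamini-Hochberg limits the expected share of false claims among all claims. It limits the chance of any false claim to 5% only when every null in the family is true. Neither document calls the secondary or tertiary step false discovery rate control. Significant secondaries from a study meant to support marketing applications could therefore be reported as controlled at 5% familywise when the method does not guarantee that.

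**The count.** The procedure compares the *i*-th smallest p-value with *i* × 0.05 / *m*. If *m* is stated as seven and the list has eight members, the decision rule for the tertiary endpoints is not fixed by the text. SAP 6 says the treatment code had not been revealed when the SAP was finalised, so the family should be fixed while that still holds.

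**Working it through.** **1. Count of the tertiary family.** SAP 9.2 states seven. The entries in SAP 8.3 are: CGI-S change, CGI-I, QIDS-SR-16 change, HDRS-21 change, HDRS-17 total score, reduction of at least 7 points, HDRS-17 category shift, and Q-LES-Q change. That is eight. SAP 11.5.5 covers the same eight. The stated seven is not reproduced.

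Seven would result from leaving out HDRS-17 total score, or from counting CGI-S and CGI-I as one (protocol 5.1.8 lists them as one item). The SAP states neither.

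**2. Effect on the cut-offs** (*i* × 0.05 / *m*):

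| Rank | 1 | 2 | 3 | 4 | 5 | 6 | 7 | 8 |
|---|---|---|---|---|---|---|---|---|
| m = 7 | 0.00714 | 0.01429 | 0.02143 | 0.02857 | 0.03571 | 0.04286 | 0.05 | – |
| m = 8 | 0.00625 | 0.0125 | 0.01875 | 0.025 | 0.03125 | 0.0375 | 0.04375 | 0.05 |

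In simulation (assumed 30% to 80% power per endpoint, correlation 0 to 0.7), counting or dropping the eighth endpoint changed at least one conclusion among the other seven in 4.7% to 12.5% of sets. Those figures ignore the gate. If the primary and all three secondaries must first succeed at 80% power each, the study-level share is about 1.1% to 5.2%.

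**3. Secondary family, exact case.** Take *m* = 3, one real effect with p near zero, and two independent true nulls. The real effect takes rank 1. A false claim arises if the smaller null p-value is at most 2 × 0.05 / 3 = 0.0333, or if both null p-values lie between 0.0333 and 0.05.

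- Benjamini-Hochberg: 1 − (1 − 0.0333)² + (0.05 − 0.0333)² = 0.0656 + 0.0003 = **0.0658**.
- Hochberg (middle cut-off 0.025): 1 − 0.975² + 0.025² = 0.0494 + 0.0006 = **0.0500**.
- Holm: 1 − 0.975² = **0.0494**.
- Two real effects: the single null is tested at 0.05, so **0.050** under Benjamini-Hochberg or Hochberg.

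**4. With correlated tests.** Two-sided z-tests, equal correlation (an assumption), gate open, real effects almost surely detected. Chance of any false claim, with simulation error of the order of 0.1 point:

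| Family | 0 | 0.5 | 0.7 | 0.9 |
|---|---|---|---|---|
| 3 secondaries, one real, Benjamini-Hochberg | 6.6% | 6.2% | 5.8% | 5.0% |
| 3 secondaries, one real, Hochberg | 5.0% | 4.8% | 4.6% | 4.1% |
| 8 tertiaries, four real, Benjamini-Hochberg | 12.0% | 10.3% | 8.7% | 6.2% |

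**5. Study level**, where the primary must also pass. Protocol 12.4 plans 80% power for it. The same power is assumed for each real effect, and the 90% and 99% rows are also assumptions. The tertiary rows take all three secondaries as real and require all three.

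| Family, power | 0 | 0.5 | 0.7 | 0.9 |
|---|---|---|---|---|
| Secondaries, one real, 80% | 4.6% | 3.8% | 3.1% | 2.5% |
| Secondaries, one real, 90% | 5.5% | 4.4% | 3.5% | 2.5% |
| Secondaries, one real, 99% | 6.4% | 5.8% | 5.1% | 4.0% |
| Tertiaries, 80% | 3.8% | 5.0% | 4.4% | 3.1% |
| Tertiaries, 90% | 7.0% | 5.7% | 4.5% | 3.1% |
| Tertiaries, 99% | 11.4% | 8.7% | 6.8% | 4.2% |

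**6. One tertiary endpoint repeats the primary.** Per SAP 11.5.5, HDRS-17 total score uses the primary model with the score in place of the change. That model has baseline as a covariate. If change = a + b·baseline + c·treatment, then score = a + (b + 1)·baseline + c·treatment, so the treatment effect c and its p-value are the same. Once the primary succeeds, this endpoint adds a small p-value to the tertiary family without adding evidence, and can raise the rank cut-offs available to the others.

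**The case against.** The strongest reply is that the secondary excess needs an unlikely configuration. Response and remission are both derived from HDRS-17, the primary scale, and are tested only after the primary succeeds. If HDRS-17 truly shifts, both are usually real, at most MADRS is null, and the rate is 5.0%. If only MADRS were real, the two nulls would come from one scale and be strongly correlated, which again pulls the rate towards 5%. At planning power the study-level rate does not exceed 5%. This stands, and it limits the size of the problem. It does not give the method a property it lacks.

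The type I error sentence names only the primary and secondary endpoints, and several tertiary endpoints are exploratory in the protocol. The 12% figure therefore does not breach an explicit promise. That also stands: the tertiary rates show what extending the hierarchy gives, not a broken claim.

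SAP 9.2 names Benjamini-Hochberg openly, and protocol 12.8.2 does the same, so an informed reader knows what is delivered. This is fair, but the stated purpose in the same paragraph still says more than the method gives.

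The 4.7% to 12.5% range for changed tertiary conclusions ignores the gate. This is correct, and the study-level range of about 1.1% to 5.2% is the better guide to how often the miscount would matter overall.

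None of these points reconciles seven with eight.

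**Conclusion.** Both parts hold. The primary analysis is unaffected.

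The count is a plain contradiction: seven stated, eight listed twice. It leaves every tertiary cut-off below 0.05 undetermined. This rests on no assumption.

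The label overstates the control within the secondary family. The excess is small: at most about 6.6% against 5%, and only with exactly one real secondary, near-certain detection and independent tests. It disappears at correlation 0.9 or when two secondaries are real, and at 80% power the study-level rate is 2.5% to 4.6%. The correlated results assume normal test statistics with equal correlation. The text should be corrected before unblinding, but the point does not threaten the main conclusion of the trial.

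**What to change.** In SAP 9.2:

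- **Label or method.** Either state that control within the secondary and tertiary families is of the false discovery rate or, if a 5% familywise claim is wanted for the secondaries, use Hochberg or Holm there. Hochberg changes only the middle cut-off (0.0333 to 0.025). At 80% power per test it lowers average power by 0.9 to 1.2 points (for example 0.777 to 0.765 at correlation 0). The tertiaries would remain under false discovery rate control.
- **Family.** Name the tertiary members so that the number matches the list. HDRS-17 total score is the natural one to leave out of the family, because it repeats the primary test; it can still be reported.
- **Optional clarifications.** State that all three secondaries must be significant before the tertiaries are tested. Name one test whose p-value enters the procedure for response and remission, since SAP 11.5.4 gives both chi-squared and Fisher. At 53 per arm, 49 of the 1,036 count pairs with chi-squared p of 0.05 or less have Fisher p above 0.05. This is an unweighted share of tables, not a probability.

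Relabelling, listing and clarifying are wording changes with no power cost. The synopsis fixed-sequence text should be aligned at the next protocol amendment, as should protocol 12.8.2 if Hochberg or Holm is chosen. Protocol 14.8 requires investigator agreement and ethics approval for an amendment. Because the SAP takes precedence, the SAP correction can go ahead first.

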10. DATA ANALYSIS SETS

Each of the following analysis sets will be evaluated for the principal statistical analyses:

10.4 Modified Young Intent to Treat Analysis Set (mYITT)

The modified younger intent-to-treat (mYITT) population will include all subjects from the ITT set enrolled in the study including subjects aged 18-21, who completed the minimal stimulation time required by the protocol and have no post randomization exclusion criteria. The mYITT analysis set will be analyzed in the treatment group as treated. Since only two subjects were under the age of 22, the mYITT set will not be analyzed separately and those subjects will not be included in the other analysis sets.

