### **12.7. Study Analysis Populations**

#### **12.7.1. Intent-to-Treat (ITT) Population:**

The intent-to-treat (ITT) population will include all subjects aged 22 through 70 enrolled in the study as randomized. This population will include all subjects who receive at least one active/sham treatment.

 Neurolief Brain Innovation	MOOD: CLINICAL INVESTIGATION PLAN	Doc No.: CL-CIP-201 Rev: REV.3 / 09June2021 Pg. 74 of 92
--	--	--

According to the ITT principle all subjects will be analyzed in the treatment group as assigned by randomization.

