#### **12.7.4. Modified Younger Intent-to-Treat (mYITT) Population:**

The modified younger intent-to-treat (mYITT) population will include all subjects from the ITT set enrolled in the study including subjects aged 18-21, who completed the minimal stimulation time required by the protocol and have no post randomization exclusion criteria. The mYITT analysis set will be analyzed in the treatment group as treated.

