#### **12.7.5. Statistical Analysis of Analysis Sets**

Safety assessments will be performed on the ITT and mYITT analysis set.

The mITT cohort will serve as the principal data analysis set for the primary and secondary statistical evaluation of the efficacy endpoints. The primary, secondary and exploratory efficacy assessment will also be performed on the per protocol (PP) analysis set as a sensitivity analysis and to show consistency of study results. The primary and secondary efficacy analyses will also be performed on the mYITT analysis set.

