10.5 Statistical Analysis of Analysis Set

Safety assessments will be performed on the ITT analysis set. The mITT cohort will serve as the principal data analysis set for the primary, secondary and tertiary efficacy endpoints analyses. The primary and secondary efficacy assessments will also be performed on the per protocol (PP) and the ITT analysis sets to show consistency of study results.

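### SAP 10.4 and 10.5 leave the two subjects under 22 out of every analysis set, safety included, although adverse events are collected for everyone enrolled

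*SAP*

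**What the plan says.** The SAP's treatment of the young subjects is in section 10.4. Its reason is that there were just two of them, and its consequence is that "the mYITT set will not be analyzed separately and those subjects will not be included in the other analysis sets". Section 10.5 names one safety population: "Safety assessments will be performed on the ITT analysis set". The SAP introduction gives the SAP precedence where it differs from the protocol.

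The protocol was wider. Section 12.7.5 reads "Safety assessments will be performed on the ITT and mYITT analysis set". The ITT set of 12.7.1 "will include all subjects aged 22 through 70 enrolled in the study as randomized", with one treatment as the exposure condition. The mYITT set of 12.7.4 starts from the ITT set, "including subjects aged 18-21, who completed the minimal stimulation time required by the protocol", and also requires no post-randomization exclusion. Section 12.4 gives the purpose of the extra cohort of up to 36: they are randomized "in the age range 18-21 to assess efficacy in this age range as well".

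The safety scope is set elsewhere. Protocol 5.1.3 and 5.1.7 and SAP 8.4 state the safety objective and endpoint without an age limit. Protocol section 11 collects adverse events for all enrolled subjects from randomization. SAP 2.2.1 says that safety was assessed in mYITT, among other sets, at the interim analysis.

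**The concern.** Safety reporting should cover everyone exposed. A subject who is too young for the efficacy set can still have an adverse event, and the number of such subjects has no bearing on whether the event should be counted. With the SAP in force, the safety denominator is smaller than the number treated, and any event in the two young subjects is missing from the numerator. The final safety analysis is also narrower than the interim one that the SAP describes.

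At stake is the completeness of the adverse event tables in a pivotal trial whose intended-use statement covers adults. A statement that safety was shown across the enrolled range of 18-70 would rest on tables with nobody under 22 in them.

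**Working it through.** **1. Who is in a safety set?**

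| Subject | Protocol 12.7.5 (ITT and mYITT) | SAP 10.4 and 10.5 (ITT only) |
|---|---|---|
| Age 22-70, one treatment | Yes, through ITT | Yes |
| Age 18-21, met minimal stimulation, no post-randomization exclusion | Yes, through mYITT | No |
| Age 18-21, treated but below minimal stimulation | No | No |

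The SAP's own ITT definition was not in the text available to me, so the age limit comes from Protocol 12.7.1. The exclusion in SAP 10.4 is explicit without it.

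**2. The protocol threshold.** Protocol 9.1.5 expects 80 min × 5 days × 6 weeks = 2400 minutes, which reproduces its figure. The minimum is 0.70 × 2400 = 1680 minutes. An 18-21 year-old therefore needed 1680 qualifying minutes to count for safety, and a 22-70 year-old needed one treatment. A subject who stopped early because of an adverse event is a natural candidate to miss that threshold. The mYITT wording also contradicts itself, because it draws on a set that excludes ages 18-21 and then includes them.

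**3. The planned young cohort.** Thirty evaluable at 15% drop-out: 30 / 0.85 = 35.3, rounded up to 36, as stated. Two subjects are 2/36 = 5.6% of that ceiling.

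**4. Effect on pooled incidence.** Assume N treated subjects aged 22-70 with incidence p, and k of the two young subjects with an event (k = 0, 1 or 2). The full-set incidence is (Np + k)/(N + 2), so the shift is (k − 2p)/(N + 2), and its size cannot exceed 2/(N + 2).

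- N = 124 (all planned subjects treated): 2/126 = 1.6 points.
- N = 106 (evaluable number only): 2/108 = 1.9 points.
- Example with N = 124, p = 10%: k = 0 gives 12.4/126 = 9.8%; k = 2 gives 14.4/126 = 11.4%.
- Worst case within an arm of 62, both subjects in it and both with an event: 10.0% becomes 8.2/64 = 12.8%, and 0% becomes 2/64 = 3.1%.

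**5. Effect on a rare event.** Suppose one of the two had the only serious device-related event.

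- As the SAP stands: 0/124, exact two-sided 95% upper limit 1 − 0.025^(1/124) = 2.9%.
- All treated subjects: 1/126 = 0.8%, exact 95% interval 0.02% to 4.3%.

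The chance that at least one of two subjects has an event is 1 − (1 − q)², where q is the true incidence: 10% at q = 5%, 19% at q = 10%, 51% at q = 30%.

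**6. What two subjects can say about ages 18-21.** With 0/2 events the exact 95% upper limit is 1 − 0.025^(1/2) = 84%. With the planned 0/30 it would have been 1 − 0.025^(1/30) = 11.6%. Adding the two back completes the reporting, but it does not characterise the age group.

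**The case against.** The strongest reply is that almost nothing changes. Under the SAP the exclusion rests on age, which is fixed before randomization, and SAP section 6 says the treatment code was not revealed up to finalization. Serious and device-related events are narrated and adjudicated, and safety data go to the DMC (Protocol 11.3.7), so a serious event in these two would not go unseen. All of this stands. It limits the harm, but none of it puts the two subjects into the incidence tables. The individual discussion of serious events in SAP 11.5.6 belongs to a safety analysis tied to ITT.

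Three further points need care:

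- **Treated or only enrolled.** SAP 10.4 says only that two subjects were under 22. That they were treated is inferred from SAP 2.2.1, which describes enrolled patients as those treated.
- **Direction.** A reader might infer that the omission can only flatter the device. That is true of event counts but not of incidence: if neither subject had an event, leaving them out raises the rate (10.0% against 9.8% in step 4).
- **The protocol's mYITT rule.** A reader might apply the 15% drop-out to 36 and conclude that about five young subjects would have been in no safety set. The documents do not support this, because drop-out and the 1680-minute threshold are different criteria. At 80 minutes a day, 7 days a week, 1680 / 560 = 3 weeks after the uncounted first week is enough, so a later drop-out can qualify. At 40 minutes, 5 days a week, seven counted weeks give 1400 minutes, so a completer can fail. The cohort was also not recruited, and the SAP supersedes the rule.

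**Conclusion.** The SAP as written gives incomplete adverse event counts: two enrolled subjects, presumably treated, are in no safety set, and the stated reason does not justify it. The bound on pooled incidence is about 1.6 points in either direction, assuming about 124 treated subjects aged 22-70 (1.9 points if 106). The practical risk is a single serious or device-related event absent from the tables.

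A reader might infer that the safety objective, or an objective for ages 18-21, can no longer be answered. The documents do not support that. The safety objective remains answerable for ages 22-70. No listed objective covers ages 18-21: that purpose appears only in the sample-size text of Protocol 12.4 and, as a past plan, in SAP 2.2.2. It failed because two subjects under 22 were enrolled against a ceiling of 36, which the SAP discloses, and no choice of analysis set would rescue it.

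**What to change.** In SAP 10.5, define a safety set of all subjects of any age who used the device, active or sham, at least once, with no compliance condition. Then:

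- Limit the exclusion in SAP 10.4 to the efficacy sets.
- Include the two subjects under 22 in every adverse event table, once their treatment is confirmed, and list their safety and efficacy data individually.
- State that efficacy at ages 18-21 was not assessed and that efficacy conclusions apply to ages 22-70.
- If the protocol text is reused, align 12.7.5 with the new safety set and correct the mYITT definition in 12.7.4.

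The cost is one analysis-set flag and a few sentences. The primary analysis, alpha and power do not change. The one drawback is a safety denominator slightly different from the ITT denominator, which a footnote can explain. If the SAP can no longer be amended, SAP 11.1 already provides for describing such a departure in the clinical study report.
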